10.4 STATISTICAL ANALYSES

10.4.1 General Approach

Prior to statistical analyses, data will be screened to assess the need for scale transformations (e.g., log, reciprocal) to normalize distributions or reduce variance heterogeneity. The study design is a two-arm randomized clinical trial with a superiority hypothesis (i.e., CRP superior to usual care). Analyses will use survival analysis and mixed effects regression with repeated measures. Follow-up assessment data will be collected from participants even if they drop out of therapy early. The primary focus will be on

Abbreviated Title: mCPT+CRP

Version Date: 07/10/25

group differences over time. All hypotheses will be two-sided at the $\alpha=.05$ level. Little's MCAR test will be used to determine if data are missing at random (Li, 2013; Little et al., 2002) and random effects pattern-mixture modeling will be used to determine if missingness influences longitudinal results (Hedeker & Gibbons, 1997; Little, 1993). The principal statistical software to be used is SAS 9.4 supplemented with SPSS, R, and MPlus.

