window (up to 42 EMA surveys per participant) for each participant: stability (i.e., the autocorrelation of scores over time), severity (i.e., mean score across all responses), and variability (i.e., the root mean square successive difference [RMSSD] across all responses). Each change index will be entered as an independent variable into a linear regression model predicting pre-post change in SSI score and a binary logistic regression model predicting follow-up suicidal behavior. To evaluate the specificity of these findings to the two weeks of active treatment, we will expand these analyses to include all 5 weeks of planned EMA data collection (i.e., 1 week prior to treatment start, 2 weeks of treatment, 2 weeks after treatment completion). This approach will allow us to distinguish treatment-specific patterns from more general patterns that signal treatment response and treatment relapse. **Power Analysis:** Power calculations for H3 were conducted using G*Power 3.1.9.2 (for suicidal ideation) and PROC POWER in the SAS 9.4 software (for suicide attempts). For the linear regression model, N=150 yielded 80% power to detect a medium effect ($R^2=0.06$) and for the binary logistic regression, N=150 provided >80% power to detect an odds ratio=1.5, assuming a conservative 20% of participants attempts suicide during follow-up.

Exploratory Research Question 1: Which subjective, objective, and treatment-related factors are most useful for predicting treatment response (i.e., change in severity of suicidal ideation) and treatment relapse (i.e., follow-up suicidal behavior)?

We will use the same analytic approach described for H3 but extend the analyses to all other variables assessed via EMA (i.e., positive and negative affect, negative thinking, and maladaptive behaviors) and Fitbit (i.e., physical activity, sleep quality). We will construct a series of models to determine which variables (and combination of variables) maximize the variance explained in pre-post change in SSI score and follow-up suicidal behavior. **Power Analysis:** Power calculations for RQ1 were conducted using G*Power 3.1.9.2. Assuming our model includes no more than 6 predictor variables, N=150 yielded 80% power to detect R^2 increases of 0.06-0.08 associated with each additional predictor variable.

Hypothesis 4: More frequent CRP use will be correlated with reductions in suicide attempts and suicidal ideation.

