We will sum the number of EMA responses during which participants endorsed the use of their CRP (and safety plan), such that higher values indicate more frequent intervention use. This count variable will be entered into a Cox regression model predicting time to suicide attempt and a linear regression model predicting change in SSI score to assess the correlation of intervention use with, respectively, follow-up suicidal behavior and severity of suicidal ideation. We will construct separate models for each treatment group. To test the specificity of our findings to CRP, we will repeat these analyses with CPT homework completion, also assessed during EMA and calculated as the sum of positively endorsed EMA responses, entered as a covariate. **Power Analysis:** The power analysis for H4 mirrors the power analysis for H3 above.

Exploratory Research Question 2: Which treatment components and design features do participants find most helpful for reducing suicidal ideation and attempts?

We will use descriptive statistics of participant characteristics, chi-squared tests, and Pearson correlations (where applicable) to explore relationships among personal experiential themes, group experiential themes, and participant characteristics. **Power Analysis:** Recommendations for minimum sample size in qualitative studies using IPA typically range from 2-25 participants, depending on the homogeneity that exists within participants' lived experience (Alase, 2017; Smith et al., 1999). Because we plan to interview all enrolled participants, our sample size will be more than adequate.

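### H3's single power figure of more than 80% cannot cover all three EMA indices on a per-SD or per-raw-unit scale; per SD it is about 50%, and the protocol does not state the unit of the odds ratio

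*Protocol*

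**What the plan says.** Protocol section 10.4.2, Hypothesis 3, reduces each participant's EMA ideation ratings to three indices: "stability (i.e., the autocorrelation of scores over time), severity (i.e., mean score across all responses), and variability", the last measured by the RMSSD. Each index enters a linear regression for pre-post change in SSI and "a binary logistic regression model predicting follow-up suicidal behavior".

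For the logistic part, the power paragraph cites a PROC POWER run and reports that "N=150 provided >80% power to detect an odds ratio=1.5, assuming a conservative 20% of participants attempts suicide during follow-up". Section 10.4.1 sets the test: "All hypotheses will be two-sided at the $\alpha=.05$ level". No unit is attached to the odds ratio, no SD or distribution is given for any index, and attrition is not mentioned for H3.

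For Hypothesis 4 the same section says only that "The power analysis for H4 mirrors the power analysis for H3 above".

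**The concern.** A 20% attempt rate in 150 participants is 30 events. That is little information for an odds ratio as modest as 1.5 on a continuous predictor, unless the predictor varies over a wide range relative to the unit of the odds ratio. The size of an odds ratio for a continuous predictor means nothing until that unit is known. Here one value is quoted for three indices with different scales.

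Predicting follow-up suicidal behavior is half of H3, and H3 is the hypothesis under Aim 2. If that half is presented as adequately powered when it is not, a null result may be read as evidence that an early marker has no value.

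**Working it through.** **Inputs.** N = 150, odds ratio 1.5 and event proportion p = 0.20 (section 10.4.2, H3); two-sided alpha 0.05, so z = 1.960 (section 10.4.1). The SD of the index divided by the unit of the odds ratio, called s below, is not in the protocol.

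**Formula.** Normal approximation for logistic regression on one continuous, normally distributed predictor:

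power = Φ( √(N·p·(1−p)) × ln(OR) × s − 1.960 )

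**Attempt to reproduce the stated figure, per SD (s = 1).**
- √(150 × 0.20 × 0.80) = √24 = 4.899, and ln(1.5) = 0.4055.
- 4.899 × 0.4055 − 1.960 = 0.026, so power = Φ(0.026) = 51%.
- Simulation with 4,000 runs: 49% (likelihood-ratio test), 48% (Wald test).

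The stated figure is not reproduced.

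**Variants on the per-SD scale.**
- 15% attrition, as assumed for H1: 150 × 0.85 = 127.5 analysed, power 45%.
- One-sided test: 63%.
- Whittemore's formula, two-sided: 44%.
- Higher event rates, two-sided: 62% at 30%, 68% at 40%, 70% at 50%.
- 50% events and a one-sided test together: 79.9%.

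None of these exceeds 80%.

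**What 80% power requires per SD.**
- Sample size: (1.960 + 0.842)² / (0.16 × 0.4055²) = 7.849 / (0.16 × 0.1644) = 298, about twice the trial. A simulation at N = 306 gave 79.8%.
- Odds ratio at N = 150: exp(2.802 / 4.899) = exp(0.572) = 1.77. A simulation at 1.8 gave 79%, so about 1.8.

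**Per raw unit.** Power now depends on s:

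| SD / unit | Power, N = 150, p = 0.20 |
|---|---|
| 0.5 | 16.7% |
| 1 | 51.1% |
| 1.25 | 70.0% |
| 1.41 | 80.0% |
| 1.5 | 84.6% |
| 2 | 97.8% |

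The threshold is s = 0.572 / 0.4055 = 1.41.

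**The three indices on the raw scale.** The mean and the RMSSD are in points of the EMA ideation score and could have an SD above 1.41. The stability index is an autocorrelation, bounded by -1 and 1, so its SD cannot exceed 1. That limit would require half the participants at each extreme. Its power is therefore at most about 51%; with an SD of 0.5 it would be about 17%.

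**The case against.** The strongest reply is that per SD is a convention brought to the text and is not in it. Section 9.2.1 (item 19) defines EMA suicidal ideation as a sum over items on several facets of ideation and names five. Section 9.3 gives the intent item a range of 0 to 4. If all five items used that range (an assumption; only the intent item is documented), the score would run from 0 to 20. An SD of 1.41 would then be about 7% of the range (1.41 / 20), in a sample enrolled for active ideation or recent suicidal behavior. With an odds ratio of 1.5 per raw point, power above 80% is quite possible for the mean and the RMSSD.

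This stands. A reader might infer from the per-SD result that the stated figure is simply false, or that no event rate could rescue it. The documents do not support that: both statements hold only per SD. The linear half of the same power statement uses a unit-free R², which makes a per-SD reading natural but does not establish it.

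The reply does not save the sentence, because the raw-unit reading that helps two indices fails for the autocorrelation. The only remaining route is a separately chosen unit for each index, such as a small fraction of the autocorrelation scale. The protocol states no such units, and an odds ratio of 1.5 would then mean a different effect for each index.

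**Conclusion.** The concern holds in a bounded form. The claim of more than 80% power cannot be reproduced from the stated inputs, and as one figure it cannot be right for all three H3 predictors on either a per-SD or a per-raw-unit scale. Per SD, power is about 50% against the stated figure of more than 80%, or about 45% with H1's attrition. Per raw unit, the claim may hold for the mean and the RMSSD but not for the autocorrelation (at most about 51%).

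These figures assume an approximately normal index, one predictor per model, 20% events and a two-sided 0.05 test.

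Two further inferences should not be drawn:
- **The 51% is not H4's power.** H4 uses a Cox model on a count of EMA responses, fitted separately in each treatment group (150 / 2 = 75 per group if allocation is equal). The model, the effect measure and the sample size all differ. For the same reason, a cross-reference to H3's calculation does not describe H4.
- **The randomized comparison is not affected.** H1 has its own power calculation, and nothing here bears on it.

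**What to change.** In section 10.4.2, Hypothesis 3, state the unit of the odds ratio and the predictor SD entered in the PROC POWER run. Then restate the power, or the odds ratio detectable with 80% power, for each of the three indices. If the per-SD scale is adopted, the statement would be: with N = 150 and a 20% attempt rate, power is about 50% for an odds ratio of 1.5 per SD, and 80% power needs an odds ratio of about 1.8 per SD. Say whether attrition is allowed for.

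Under Hypothesis 4, replace the cross-reference with a power statement for the per-group Cox model on the count of intervention use.

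This is a change of text only, with no extra participants and no change to the design. The cost is that the stated figure becomes less favourable, on the per-SD scale for every index and on the raw scale at least for the autocorrelation.

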4.2 SCIENTIFIC RATIONALE FOR STUDY DESIGN

[figure not shown]
Treatments that rapidly reduce suicidal *ideation* also reduce suicidal *behaviors*. Results of a previous RCT indicates CRP rapidly reduces suicidal ideation and suicide attempts among military personnel, but additional studies of CRP are needed to evaluate the intervention's effectiveness in a broader range of clinical settings and populations. Pilot data collected by our team indicate that, as compared to usual care suicide risk management, CRP accelerates reductions in suicidal ideation and reduces suicidal behavior among military personnel and veterans receiving treatment for PTSD. This study will build on these promising findings to further test the effectiveness of CRP on suicidal ideation and suicidal behaviors when combined with massed CPT for PTSD. This study will also investigate early indicators of treatment response (i.e., reductions in suicidal ideation) and treatment relapse (i.e., suicidal behavior), thereby providing critical information for developing novel decision-making tools for clinicians working with high-risk patients.

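### Exploratory RQ1 selects predictors by maximum variance explained with no correction for the search, so the selected model's apparent fit is optimistic and the stated power does not carry over to it

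*Protocol*

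**What the plan says.** The relevant text is in Protocol section 10.4.2, under the first exploratory question: "Exploratory Research Question 1: Which subjective, objective, and treatment-related factors are most useful for predicting treatment response" and relapse.

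- **Method.** "We will use the same analytic approach described for H3". H3 reduces each participant's EMA series to three indices (stability, severity, variability) and enters them in a linear regression for pre-post SSI change and a logistic regression for follow-up suicidal behavior.
- **Candidates.** Two Fitbit measures, one of activity and one of sleep, join the pool. For EMA, the plan is to "extend the analyses to all other variables assessed via EMA (i.e., positive and negative affect, negative thinking, and maladaptive behaviors". No count of candidate predictors is given.
- **Selection rule.** The team will "construct a series of models to determine which variables (and combination of variables) maximize the variance explained" in the two outcomes. No hold-out sample, resampling, shrinkage or adjusted measure is named.
- **Power.** "Assuming our model includes no more than 6 predictor variables", N=150 is said to give 80% power for R² increases of 0.06-0.08, worded as belonging to each further predictor.
- **Time windows.** H3, whose approach RQ1 adopts, is also to be repeated over a longer period: "we will expand these analyses to include all 5 weeks of planned EMA data collection".

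Section 4.2 says that the study's work on early indicators is "providing critical information for developing novel decision-making tools for clinicians working with high-risk patients".

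**The concern.** Variance explained in the data used for fitting never falls when a predictor is added. It rises further when the predictors are chosen because they fit those data best. A rule that takes the maximum over variables and combinations therefore rewards chance fit. If the winning model is then described by the same R², or tested by an ordinary F test on the same data, the result is too favorable and the chosen set is unstable.

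The power statement has a related weakness. A regression power calculation of this kind treats the tested predictors as known before the data are seen. It says nothing about predictors picked as the best of a larger pool.

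At stake is how RQ1 will be read. The protocol wants early markers of response and relapse in a high-risk population. A chance model that appears to explain 9% or more of the variance could be taken forward as a signal.

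**Working it through.** **1. Inputs**

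- N=150, at most six predictors, 80% power, R² increase 0.06-0.08: section 10.4.2, RQ1.
- Two-sided alpha 0.05: section 10.4.1.
- Named domains: positive affect, negative affect, negative thinking, maladaptive behaviors (EMA); physical activity, sleep quality (Fitbit). That is 4 + 2 = 6.
- Indices per domain: 3, carried over from H3. *Assumption:* 6 × 3 = 18 candidates. If both time windows are searched, 18 × 2 = 36. With one index per domain the pool is 6. The range 6 to 36 is shown.
- Sensitivity: 15% attrition, stated for H1 only, gives 150 × 0.85 ≈ 127.

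**2. The plan's own power figure**

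Noncentral F test of u predictors, with f² = R²/(1 − R²), noncentrality = f² × N, and degrees of freedom u and N − u − 1. R² detectable with 80% power at N=150:

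| u | 1 | 2 | 3 | 4 | 5 | 6 |
|---|---|---|---|---|---|---|
| R² | 0.050 | 0.062 | 0.070 | 0.076 | 0.082 | 0.087 |

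The stated 0.06-0.08 matches a joint test of two to five predictors (power 78.9% at 0.06 with u=2; 79.0% at 0.08 with u=5). On the literal wording, one added predictor, power would be 86.7% at 0.06 and 94.8% at 0.08. On either reading the tested predictors are fixed in advance.

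**3. What the rule returns when nothing predicts**

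Outcome and candidates are simulated as independent, and six predictors are chosen by forward selection. R² is the total for the selected model. The F test is the ordinary one, F = (R²/6) / ((1 − R²)/(n − 7)), which at n=150 is significant when R² exceeds about 0.083.

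| Candidates (n=150) | Mean total R² | F test significant |
|---|---|---|
| 6 | 0.04 | 5% |
| 9 | 0.06 | 16% |
| 12 | 0.07 | 29-34% |
| 18 | 0.09-0.10 | 59-63% |
| 36 | 0.13-0.14 | 96% |

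Ranges show differences between simulation runs and settings.

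- With six candidates there is no selection. The expected R² is 6/149 = 0.040 and the F test holds its 5% level. What lies above that line is due to the search.
- An exhaustive search over all sets of 6 from 18 gives 0.094, so forward selection is a fair stand-in.
- Correlation of 0.5 between candidates leaves the 18-candidate total at 0.095.
- At n=127 with 18 candidates the total is 0.11.

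**4. Per predictor**

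At n=150 with 18 independent candidates, the six successive noise increments average 0.032, 0.020, 0.015, 0.012, 0.009 and 0.007 (sum 0.095). The best single noise predictor reaches 0.06 in about 3-5% of runs. The chance that at least one of 18 independent noise candidates has p<0.05 is 1 − 0.95^18 = 60%.

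**5. Suicidal behavior**

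At the 20% attempt rate assumed for H3, 150 × 0.20 = 30 participants have an event. Selecting six of 18 noise candidates then gives an apparent AUC of about 0.71, against a true 0.50.

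**The case against.** - **Unlike quantities.** A reader might infer that noise will appear to explain more than the effects RQ1 is powered for, since 0.09-0.10 exceeds 0.06-0.08. The documents do not support that. The protocol words its figure as an increase for each additional predictor, while 0.09-0.10 is a six-predictor total. Per predictor, noise averages about 0.03 at best. The joint reading fits the stated power better, but it is not what the text says. This objection stands.
- **Assumed pool and search.** Neither the 18 candidates nor a search of every combination is stated. A series of models could be built sequentially, and six is a ceiling in a power assumption rather than a required size. With six candidates there is no inflation from selection. This stands, and is why a range is shown.
- **Attempt rate.** The protocol calls 20% conservative, and section 10.4.2 uses 30-50% in usual care for H1. More events would reduce the AUC optimism, so the 0.71 is illustrative only.
- **Clinical use.** A reader might infer that the selected model is to become a decision tool. Section 4.2 speaks of the study's early-indicator work as a whole and does not name RQ1. This stands.
- **Exploratory, and a SAP may exist.** RQ1 is labelled exploratory, and validation detail is often left to a SAP. This limits the severity. It does not remove the point, because the protocol states a selection criterion, and an analysis that follows that sentence as written inherits the optimism.

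**Conclusion.** The concern holds in a limited form. The protocol fixes a maximising criterion and names no correction for the search. Whenever the candidate pool exceeds six, the apparent performance of the chosen model will be optimistic. If the pool is about 18, a model built from noise alone would show a total R² of about 0.09 at n=150 and pass a naive F test in about 59% of runs. Across 6 to 36 candidates the figures run from 0.04 and 5% to 0.13 and 96%. They assume independent noise, six predictors chosen by forward selection, and the same data used for selection and scoring.

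The 80% power for increases of 0.06-0.08 applies to pre-specified predictors only. It is not shown that noise reaches that size for a single predictor; typically it does not.

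Severity is low to moderate. RQ1 is exploratory, and neither H1 nor H2 depends on it.

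**What to change.** In section 10.4.2, RQ1, replace the maximising criterion with a statement on these lines: model performance will be reported as cross-validated or bootstrap optimism-corrected R² for SSI change, and as AUC and calibration corrected in the same way for suicidal behavior, with the whole variable selection repeated inside each resample. Penalised regression such as elastic net is one suitable selection method but is not essential.

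State the number of candidate predictors (domains, indices and time windows). Add that the 0.06-0.08 power figure applies only to predictors specified in advance.

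The cost is a few hours of programming in software the protocol already lists (R, SAS), and a lower reported R². No new data, visits or participants are needed.

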6.6.2 CompensationN/A

- Participants can be compensated for completing follow-up assessments using the following schedule:
 - \$50 for the posttreatment qualitative interview
 - \$25 at 1 month
 - \$25 at 3 months
 - \$25 at 6 months
 - \$25 at 9 months

Abbreviated Title: mCPT+CRP

Version Date: 07/10/25

- \$50 at 12 months

Participants will also be compensated for completing EMA surveys and wearing their Fitbits.

Participants will be compensated based on the number of EMA surveys completed per week:

- \$20 per week for completing at least 75% of EMA surveys (32 of 42 surveys) and wearing their Fitbit at least 75% of days (5 of 7 days) per week (total \$80 for the four weeks) or
- \$30 per week for completing at least 90% of EMA surveys (38 of 42 surveys) and wearing their Fitbit at least 90% of days (6 of 7 days) per week (total of \$120 for the four weeks).

This yields a maximum possible compensation of \$120 for EMA completion and Fitbit wear, totaling \$320 of possible compensation for all study activities. Participants will be allowed to keep the Fitbit.

- As required by UTHSCSA, these funds will be distributed using the university ClinCard system.
- Payment will be provided via a rechargeable MasterCard® ClinCard. The MasterCard® ClinCard is a debit card issued to the study participant. Funds are loaded onto the card through the ClinCard website at www.clincard.com. Only authorized users are able to access the ClinCard website with a username and password to add funds. The ClinCard funds will typically be available to recipients within one business day but payment could take up to 2 weeks. ClinCard funds can be used as the participant chooses. The participant will be notified that their name, social security number, address and date of birth will be shared with a third-party (ClinCard) for the purposes of payment processing. This information will be used for the administration of the payment and will be kept strictly confidential.

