7.1.2 Administration

Massed Cognitive Processing Therapy (mCPT)

Abbreviated Title: mCPT+CRP

Version Date: 07/10/25

All participants will meet with their assigned research therapist for an initial 1½ -hour “intake” session during which the research therapist will provide information about the massed therapy protocol, schedule dates and times for massed CPT sessions, conduct a suicide risk assessment, and administer the randomly assigned suicide risk intervention. CPT sessions will be scheduled daily for 10 consecutive business days (i.e., “massed” CPT), with the first appointment being 1-2 weeks post-intake. The CPT session content is summarized in Table 1. Participants will be allowed to schedule up to 3 optional “booster sessions” during the follow-up year to review skills learned in therapy and receive additional support and/or coaching after the acute treatment phase.

Table 1. Massed CPT Session Content

Session No.	Session Focus
1	Education about PTSD
2	Impact Statement #1, ABC
3	Challenging Quest.
4	Patterns of Prob. Thinking
5	Challenging Beliefs, Safety
6	Trust
7	Power & Control
8	Esteem
9	Intimacy
10	Impact Statement #2

Crisis Response Planning (CRP).

CRP entails a collaborative process wherein a suicidal person provides a narrative description of a recent suicidal crisis or acute period of emotional arousal then creates a plan that lists indicators of acute affective arousal (i.e., “warning signs”) and strategies the person could use to regulate this arousal (e.g., self- management strategies, reasons for living, sources of social support, professional support. With assistance from their research therapist, participants will handwrite a crisis response plan on an index card. Consistent with the intervention’s design, participants will be asked about CRP use during each massed CPT session as part of homework review.

Usual Care.

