19. Ecological Momentary Assessment (EMA). This study will utilize EMA to assess participants' behaviors, mood, and social context in real time in participants' natural environments. Positive and negative mood state will be assessed using 15 items to assess affect, some drawn from the Positive and Negative Affects Scale (PANAS; Watson et al., 1988). Social context will include researcher-developed items to assess who participants are with and perceived closeness to other people. Suicidal ideation will be assessed using a sum score of items assessing various facets of ideation including wish to live, wish to die, suicidal intent, feeling that life is not worth living, and thoughts about suicide. Consistent with best-practice recommendations (Conner & Lehman, 2012), we will employ a mixture of fixed time-based sampling and experience sampling. A fixed time-based survey will be administered every morning to assess the occurrence of variables during the preceding night or prior day, and experience sampling will be used to deliver five standardized surveys, distributed quasi-randomly during each day (<5 minutes to complete). The protocol for these prompts draws from items from a battery that measures: 1) select items assessing current positive and negative affect and rumination; 2) items measuring suicidal ideation and behavior; 3) items measuring substance use; 4) behavioral and contextual factors that can impact risk/resilience for our outcomes of interest (i.e., stressful situations, social engagement), 5) sleep characteristics, and 6) crisis response plan use.

Please note that while all of the possible 96 questions are being submitted for regulatory reviews, a selection of questions 1-50 will be administered each morning during EMA and a selection of questions 1-46 (starting on page 7) will be administered the other times throughout the day.

Participants will respond to EMA prompts through their smartphone. Participants will be trained to complete the EMA procedures by study staff who will lead participants through a training demo to ensure that participants understand how and when to answer questions through EMA. EMA prompts will be randomly delivered throughout the day, with no scheduled differences between weekend and weekday prompts. To offset participant reactivity, question sets will be administered in a random

Abbreviated Title: mCPT+CRP

Version Date: 07/10/25

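### Hypothesis 4 enters a raw count of plan use with no adjustment for need, so crisis frequency confounds its association with attempts and with SSI change

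*Protocol*

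**What the plan says.** Protocol section 10.4.2 states the hypothesis with a direction: "More frequent CRP use will be correlated with reductions in suicide attempts and suicidal ideation". It then fixes the exposure: "We will sum the number of EMA responses during which participants endorsed the use of their CRP (and safety plan". The resulting total is taken at face value, "such that higher values indicate more frequent intervention use". On the model it says "This count variable will be entered into a Cox regression model predicting time to suicide attempt", with a parallel linear regression on change in SSI, and each arm is modelled separately. The only covariate named is CPT homework completion. It appears in a repeat analysis and is itself a total, "calculated as the sum of positively endorsed EMA responses, entered as a covariate".

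Three other places bear on this:
- Section 7.1.2 describes the content of the plan as warning signs plus "strategies the person could use to regulate this arousal", meaning acute emotional arousal.
- Section 9.2.1 lists, in the same EMA battery that records plan use, "items measuring suicidal ideation and behavior".
- Hypothesis 3 (sections 3, 10.1 and 10.4.2) expects milder risk features during treatment to predict response and the absence of later suicidal behaviour. It uses mean EMA ideation as one predictor.

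**The concern.** A tool for acute arousal is used more often by people who have more acute arousal. If those people also attempt more often, as Hypothesis 3 expects, the count carries two signals of opposite sign: willingness to use the plan in a crisis, and the number of crises. The Hypothesis 4 models contain nothing that separates them. The Hypothesis 3 predictor that would help, EMA ideation, is collected but not used here.

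Aim 3 seeks features that influence effectiveness, so the Hypothesis 4 coefficient will be read as evidence on whether using the plan helps. A null or reversed coefficient for attempts could arise from need alone. A favourable coefficient for SSI change could also arise without any effect of use.

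**Working it through.** The protocol states no figure for this analysis that could be reproduced, so the check is by simulation. From the protocol: 6 surveys a day for 28 days, 6 × 28 = 168 offered; about 75 per arm (150 split equally); models fitted by arm. Everything else is assumed.

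**Simulation A (Cox model).** Latent severity S drives the number of crises (Poisson, mean 12 in 28 days, log-scale slope 0 to 0.75 per SD) and the attempt hazard (HR 1.0 to 2.0 per SD). The propensity to use the plan in a crisis is truly protective, HR 0.70 per SD. About 75% of surveys are answered, and about 27 to 30% attempt within a year. Large-sample HRs per SD, with answering unrelated to severity:

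| Slope of crises on S | HR of S | Raw count | Count ÷ surveys answered | Count + S | Use as share of crises |
|---|---|---|---|---|---|
| 0 | 1.0 | 0.799 | 0.794 | 0.799 | 0.789 |
| 0.25 | 1.5 | 0.942 | 0.942 | 0.796 | 0.792 |
| 0.25 | 2.0 | 1.031 | 1.030 | 0.801 | 0.782 |
| 0.5 | 1.5 | 1.054 | 1.056 | 0.779 | 0.783 |
| 0.5 | 2.0 | 1.210 | 1.221 | 0.795 | 0.797 |
| 0.75 | 2.0 | 1.246 | 1.259 | 0.813 | 0.815 |

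The first row is the benchmark. Even without confounding the count recovers about 0.80 rather than 0.70, because it measures propensity with noise. The last two columns return to that benchmark. The fourth does not.

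With 75 participants in an arm (1,500 simulated trials per setting), the raw-count estimate exceeds 1 in 58% (slope 0.5, HR 1.5), 81% (0.5, 2.0) and 90% (0.75, 2.0) of trials. It is significantly harmful in 6%, 20% and 37%. With no crisis-severity link and severity HR 1.0, the figures are 14% and 0.1%.

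**Simulation B (Cox model, different structure).** Crisis frequency itself raises the hazard, and the true use effect is HR 0.6 per SD, n = 75. At crisis HRs of 1.0, 1.35 and 1.65 per SD, the raw count gave 0.79, 0.99 and 1.13. Use per completed survey gave 1.15 where the raw count gave 1.13. Adjusting for baseline SSI alone gave 1.07. Use per crisis-positive survey with crisis frequency in the model gave 0.66 to 0.69.

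**Survey completion on its own.** The total has no denominator. At an assumed 10% endorsement rate, 90% completion gives 168 × 0.9 × 0.1 ≈ 15 endorsements and 50% gives 168 × 0.5 × 0.1 ≈ 8, at identical use. With crisis probability held constant and only completion varying (true HR 0.6 per SD), the raw count gave 0.73 against 0.70 per answered survey. That is slight dilution with no change of sign.

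**SSI-change model.** With no true effect of use, and SSI improving by 20 to 60% of underlying severity, the raw count correlated +0.19 to +0.46 with improvement. Participants with more crises may start higher and have further to fall.

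**The case against.** Hypothesis 4 is worded as a correlation, sits under Aim 3, and leaves the randomised comparisons alone. The protocol nowhere says that a positive coefficient would be taken as harm. Section 7.1.2 also has plan use reviewed at every CPT session as part of homework, so some endorsed use may be routine practice unrelated to crises, which would weaken the confounding. And no crisis rate, use rate or crisis-attempt association is given, so any size is assumed. All of this stands, and it limits the point to what can happen. It does not rescue the exposure, because the hypothesis is directional and the omitted variable is one that the protocol itself expects to predict attempts.

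A reader might go further and blame uneven survey completion. Section 6.6.2 expects it, with a payment tier for "completing at least 75% of EMA surveys (32 of 42 surveys", and dividing by surveys answered looks like the remedy. The calculations do not support that. Completion mainly adds noise, and if more severely ill participants answer less, it nudges the estimate slightly towards protection. The homework total may even stand in partly for completion, but only in the repeat analysis, and it says nothing about need.

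**Conclusion.** The point holds as confounding by need. In the Cox model the raw count can pull a truly protective association to null or past it: about 0.94 to 1.05 under moderate assumptions, 1.21 to 1.25 under strong ones, and the right direction (0.76 to 0.81, over all severity HRs and both answering patterns tried) if crises are unrelated to severity. These figures depend on assumed crisis and use rates.

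Two stronger inferences are not supported. One is that Hypothesis 4 is biased against the plan throughout; in the SSI-change model the bias may flatter it. The other is that the trial's main conclusion is at risk; Hypotheses 1 and 2 compare randomised arms and do not use this count. The point is worth correcting because the exposure is fixed in the protocol text and the data to repair it are already being collected.

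**What to change.** In both Hypothesis 4 models, add a term for need:
- Preferably define the exposure as the proportion of ideation- or distress-positive EMA surveys at which the plan was used, with the frequency of such surveys as a covariate. Fix the definition of a positive survey in advance.
- Add baseline SSI to the SSI-change model.
- Keep the raw count as a sensitivity analysis, and describe the Hypothesis 4 results as associations.

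The change is analysis wording plus a derivation from existing data. It has three costs:
- **Few events.** With 20 to 30% of 75 attempting, an arm has 0.20 × 75 = 15 to 0.30 × 75 ≈ 23 events. The Cox model should carry only one or two adjustment terms: exposure plus two leaves roughly 5 to 8 events per parameter.
- **Mediation.** Momentary ideation may lie partly downstream of plan use, so a version adjusted for baseline SSI only should be reported alongside, with the caveat that it corrects only in part.
- **Undefined proportions.** Participants with no positive survey have no proportion. A supporting model with the raw count, the number of positive surveys and the number answered keeps them; the corresponding model in simulation A gave 0.76 where the raw count gave 1.21. It uses two adjustment terms.
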